4.4 Exclusion criteria

- Unable or unwilling to partake.
- In the opinion of the patient's treating physician, the patient has another condition which is significantly impairs their ability to take part in the BR.
- No access to the internet or appropriate IT equipment

4.5 Recruitment and consent

Patients attending a regional severe asthma service who have undertaken a systematic multidisciplinary assessment will be identified as eligible to participate by a health professional familiar with them. This multidisciplinary review is part of normal clinic practice for the identification and treatment of severe asthma patients.

By post - Patients identified as eligible to participate will be sent a Letter of Invitation (Appendix 3) by their clinician. The letter will also include a study Participant Information Leaflet and Consent Form (Appendix 4), a General Symptom Questionnaire (GSQ) and a prepaid return envelope to be used to return the completed consent form and GSQ to the patient's clinician at RD&E (study information pack). The Patient Information Leaflet includes the phone number details for the research team. The information leaflet will inform patients that they are welcome to contact the researcher if they have any questions about the

research that may be preventing from agreeing to participate. Participants will have all of their questions answered before they sign a consent form.

Patients will be asked to return a completed Consent Forms within two weeks.

The information leaflet explains that the GSQ that the patient completes will be used as an additional screening tool to assess the number of non-respiratory symptoms they experience each week.

In clinic – Alternatively, eligible patients will be able to consent to take part in the study during a clinic appointment. When possible, patients identified as eligible to participate will be contacted by a health professional two weeks before they are due to have an asthma clinic appointment (remote or face to face) and invited to participate. This contact will be made by posting a Patient Invitation Letter (Appendix 3) and Patient Information Leaflet including a consent form (Appendix 4) out to the patient. The Invitation Letter and Patient Information Leaflet will include instructions to read the material carefully and to bring the consent form with them to their next scheduled clinic appointment. Contact details for the PI, and researcher will be included on the Patient Information Leaflet and can be contacted in the case that the patient has questions.

If it is not possible to contact patients prior to the clinic appointment, they will be informed about the study during their remote or face to face appointment. At the consultation, patients who have been identified as eligible will be invited to participate. If they accept, a health professional will introduce the patient to a researcher who provides the patient with information on the study and a Participant Information Leaflet. The patient will have the opportunity to take this leaflet away with them and to think about participating before signing a consent form. A completed consent form can then be returned using a FREEPOST envelope if the patients decides to participate. Alternatively, the patient will be able to complete the consent form before leaving clinic.

Once a patient has provided a completed consent form, they will be given be given a GSQ to complete.

The Patient Information Leaflet will outline what would be expected of the patient if they chose to participate including an outline of what the Body Reprogramming course involves and how

those who participated will be invited to a focus group at the end. During the project a video of the impact of severe asthma on patients and how this may be addressed by BR will be developed and will be available as an additional online information resource to patients and their families. The Patient Information Leaflet will also contain a contact number for a member of the research team if they have any questions. If a patient wants to participate, they will be asked to provide written informed consent which includes agreement to take part in the four-week trial of BR and the post-trial focus groups or one to one interview.

4.6 Data collection Methods

Four-week trial of BR.

The intervention

Body Reprogramming will be delivered to two groups of patients. The maximum group size will be 8 patients to allow time for questions from participants. The intervention will be delivered via the Zoom video call platform. There will be four sessions and each session will consist of a 25-30 minute presentation. At the end of the presentation there will be an opportunity for patients to ask questions or raise points of interest. Each session will include a 'practice and report back next week' instruction. Participants will be provided with a list of web resources for tai chi, guided imagery, yoga and the Alexander technique (Appendix 5) and information on the course (Appendix 6). See Appendix 4 for further course details.

4.7 Data collection time points

Participants will be asked to complete a series of questionnaires (see section 4.8) when they attend the Body Reprogramming course during the first and last week. These will be posted to the participant's home address by a research nurse, completed, and returned to the patients' clinic using a FREEPOST envelope.

At the end of the course, participants will be asked to complete a course feedback form.

If participants have not returned the questionnaire within two weeks the questionnaire pack will be sent out again. If a further two weeks pass without the return of questionnaires a researcher will contact participant by phone and ask if they need assistance.

Patients will be asked to text or email the course co-ordinator if they are unable to attend a course date for any reason. Experience shows that health and other problems can prevent patients from attending, so attendance monitoring requires this form of data.

Demographic data

The following demographic and clinical information will be collected from the participants' clinical records at baseline by a researcher:

Patient demographics:

- Age
- Sex
- Ethnicity
- Smoking status

Clinical data

Most recent spirometry (in the last 6 months),

Major co-morbidities (respiratory and non-respiratory as identified by the patient's clinician)

- Current Drug treatment
- Asthma exacerbations requiring systemic steroids in the last 12 months,
- Cumulative steroid burden in the last 12 months,
- Healthcare utilisation: hospital admissions / Emergency Department attendances in the last 12 months.

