1.2 Rationale for Current Study

When assessing the impact of management and treatment interventions aimed at improving HRQoL, it is important to look beyond the lung. In a cross-sectional study of severe asthma, we found that the frequency of extra-pulmonary symptoms significantly increased with the cumulative burden of systemic corticosteroids. However, those patients on biologic treatments had lower symptom scores irrespective of their systemic steroid burden (4).

We hypothesize that a specific intervention aiming to optimising patient knowledge on disease management, physical activity, relaxation (5) and other psychological and biological lifestyle changes that increase well-being and mood, may lead to improved self-management. Severe asthma patients lack any form of rehabilitation provision analogous to pulmonary rehabilitation, which is an evidenced-based education and exercise programme for people with COPD and has additional benefits on top of drug therapies (6). Indeed evidence shows that pulmonary rehabilitation should be provided prior to stepping up drug treatments in COPD , leading to the hypothesis that a similar provision for severe asthma patients prior to

starting new treatments such as biologics would enhance response to treatment. Furthermore there is emerging evidence that pre-habilitation improves outcomes in high risk patients undergoing surgery and is now being recommended to improve resilience in the face of the SARS-CoV-2 pandemic (7). BR may well act as a strategy to promote resilience to Coronavirus amongst an at risk group of severe asthma patients.

We hope to see greater HRQoL improvements from severe asthma patients who have been “primed” by an education and behaviour change programme when they start biologics. Biologic therapies have a highly specific mode of action and may therefore interact positively with any reduction in systemic inflammation resulting from lifestyle improvement. We have provided a detailed theoretical rationale for potential mechanisms (8).

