This questionnaire contains 7 items and takes into consideration FEV1% predicted and daily use of rescue bronchodilator. Patients respond to 7 items concerning their symptom severity on a 0-6 scale (0 = no impairment, 6 = maximum impairment) (14). The questionnaire asks patients to assess their symptoms over the last week.

Note: the included questionnaires are available and validated in the majority of European languages and many non-European ones. However, if a participant requires a translation of a questionnaire that is not available, they will not be asked to complete the particular questionnaire.

Post course questionnaires

Global Rating of Change Questionnaire – Phase one (Appendix 12)

This scale will be used by participants to indicate how much better they feel since commencing a BR. The 11-point scale ranges from -5 (a great deal worse) to 5 (A great deal better) (15). The time scale is between before the start of treatment and the current assessment.

All questionnaires are presented in paper and pencil format, to be self-completed by the patient but with support if needed.

Friends and Family Test (FFT) (Appendix 13)

This is a one question questionnaire used throughout the NHS to assess patient's thoughts on a health service they regularly use. The question we will use in the FFT asks "We would like you to think about your recent experience of our Body Reprogramming. How likely are you to recommend Body Reprogramming to friends and family if they needed a similar service?

" Participants will respond on a 5 point scale from "Extremely Unlikely" to "Extremely Likely".

Questionnaire completion

Data on the number and percentage of questionnaires collected at the two time points will be recorded. This data will inform participants' willingness to complete the above questionnaires.

Post-trial focus groups or interview

Focus groups will consist of 3-6 participants and moderated by one of the members of the research team with qualitative research experience (LC, MH, JL). Two focus groups will be

conducted in total, and will explore the experience of participants after participating in a four-week trial of BR.

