5.5 Recruitment and consent

Before commencing a biologic treatment for severe asthma in normal clinical care, patients are reviewed by a Multi-Disciplinary Team (MDT) responsible for their care. The PI at the participating hospital will identify patients eligible to take part in this study at this time. Recruitment of eligible patients will then proceed as outlined in phase one. Participants will be sent a Patient Invitation Letter (Appendix 14) and Patient Information Leaflet (Appendix 15) that describe phase two of the study.

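### Section 4.7 sends the Friends and Family Test to the treating clinic and gives the course feedback form no return route, leaving a risk, of unknown size, of over-favourable acceptability ratings

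*Combined protocol and SAP*

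**What the plan says.** **Return route.** Section 4.7 refers to the questionnaires of section 4.8, has them posted to the home by a research nurse, and has them "returned to the patients' clinic using a FREEPOST envelope". Section 4.8 includes the FFT among the post-course questionnaires. Its item opens "We would like you to think about your recent experience of our Body Reprogramming" and asks "How likely are you to recommend Body Reprogramming to friends and family if they needed a similar service", on a 5-point scale. Forms are on paper, "to be self-completed by the patient but with support if needed".

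**Feedback form.** Section 4.7 adds: "At the end of the course, participants will be asked to complete a course feedback form". It does not say who receives the form, how it is returned, or whether it carries a name.

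**Focus groups and interviews.** Under 4.8, focus groups are "moderated by one of the members of the research team with qualitative research experience". Three people are listed by initials, and all three are among the five analysts listed in 6.7.

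**Phase 2.** Section 5.6 keeps the Phase 1 time points and outcome measures. Under 5.5, patients are found when the multidisciplinary team reviews them before a biologic: "The PI at the participating hospital will identify patients eligible to take part in this study at this time".

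**Safeguards.** Study IDs replace names (6.5). Access is limited to the research team, and a file linking IDs to clinical numbers is held at the hospital (6.7). Patients are told that the researchers are not acting as clinicians (6.1). Discussion is led by participants, and those who decline a group may have an interview (4.8).

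**The concern.** Acceptability is an aim of both phases (4.1, 5.1). Phase 1 feedback is used to change the course before Phase 2, and Phase 2 is meant to inform a possible randomised trial. A patient who found the course unhelpful is asked to say so on a form addressed to the clinic that invited them and continues to treat them. Some patients may soften their answer.

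There is no comparison arm in which such a tendency could cancel, and no independently collected rating against which to check it. If it occurs, criticism that should reshape the course is lost, and the FFT and written feedback look better than patients' real views. The same question arises, less directly, for focus groups run and analysed by the study's own team.

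**Working it through.** **1. Which acceptability evidence follows the clinic route?**

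| Evidence | Return or collection | Depends on a stated opinion of BR? |
|---|---|---|
| FFT | Clinic, through the 4.7 reference to 4.8 | Yes |
| Course feedback form | Not stated | Yes |
| Focus groups and interviews | Research team member | Yes |
| Global Rating of Change | Clinic, through the same reference | No: it rates how much better the patient feels |
| Attendance and completion counts | Study records | No |

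The exposed items are therefore the FFT, the feedback form if it goes the same way, and, through a different mechanism, the focus groups and interviews. Section 4.7 speaks of first-week and last-week packs, while the FFT is listed as post-course, so its route is a plain reading of the cross-reference and not an explicit statement.

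**2. How far do the safeguards reach?** Study IDs hide the name on the form, but the link file exists and the patient sees where the envelope goes. Section 6.7 limits access to the research team, but 4.7 has the envelope arrive at the clinic, and neither section says who opens it or whether any treating clinician is on the team. Home completion removes the face-to-face element, except where support is given; the plan does not say by whom. The statement in 6.1 about researchers' roles does not cover a form sent to clinicians.

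**3. Number of respondents.** Section 4.10 plans 12-14 participants with 10% withdrawal and at least 10 completers. Completers = N × (1 − 0.10):
- N = 12: 12 × 0.90 = 10.8, or 10 whole participants
- N = 14: 14 × 0.90 = 12.6, or 12 whole participants

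The plan's figure of at least 10 is reproduced.

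**4. Weight of one answer.** One respondent who moves from not favourable to favourable shifts the share by 100/n points: 100/10 = 10.0, 100/12 = 8.3, 100/14 = 7.1.

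**5. Illustration of a bias.** Let p be the true favourable share and f the fraction of the others who answer favourably anyway. Both are assumptions; the documents give neither. The expected observed share is p + (1 − p)f, so the bias is (1 − p)f. In percentage points:

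| p | f = 0 | f = 0.10 | f = 0.25 | f = 0.50 |
|---|---|---|---|---|
| 0.5 | 0 | 5.0 | 12.5 | 25.0 |
| 0.6 | 0 | 4.0 | 10.0 | 20.0 |
| 0.7 | 0 | 3.0 | 7.5 | 15.0 |
| 0.8 | 0 | 2.0 | 5.0 | 10.0 |

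**6. Could the data reveal it?** If 8 of 10 were favourable, the exact 95% interval would be 44% to 97%, wide enough to hide any bias in the table. A larger sample would narrow the interval but leave the bias in place, because (1 − p)f does not depend on n. It has to be prevented at collection.

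**The case against.** The strongest case against is that this is a 12-14 person feasibility phase, that team-run qualitative work is ordinary at this stage, and that several safeguards exist. No FFT threshold is set, so no stated decision turns on a few points. Assurances about confidentiality and care may also sit in the leaflets or on the FFT form (Appendices 4, 13 and 15), which are not in the text reviewed. All of this stands, and it limits the point to a risk with an inexpensive remedy.

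A reader might go further in five ways that the documents do not support:

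- *The acceptability result is biased.* Nothing shows or sizes a bias. The table above includes zero.
- *Patients must criticise the course in front of those who offered it.* The forms are posted and self-completed, and the plan does not say who delivers the course or that deliverers moderate.
- *The moderators developed BR.* The team writes "We have provided a detailed theoretical rationale for potential mechanisms" in section 1.2, but that sentence closes a paragraph on how biologics may interact with lifestyle improvement. It speaks for the team as a whole and does not establish the role of each listed moderator.
- *Phase 2 is worst affected, because the clinic controls the biologic.* Section 5.3 requires approval for the biologic before BR is offered, and 5.5 concerns finding eligible patients, not handling feedback. Greater pressure in Phase 2 is conjecture.
- *The whole feasibility result is affected.* Section 4.2 also relies on attendance and plans to speak with people who did not attend. Counts of attendance and completion do not rest on ratings.

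What survives is narrower. A form that rates the course goes to the treating clinic, the written feedback has no stated route, and no rule separates moderation or coding from course development or delivery.

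**Conclusion.** The concern holds as a risk of over-favourable FFT and written-feedback results, with a secondary risk in the focus groups. Its size is unknown. Each changed answer is worth 7.1 to 10.0 percentage points for 14 down to 10 respondents; the larger shifts in the table rest on assumed values of p and f. The conclusion assumes that the FFT follows the route 4.7 gives for the section 4.8 questionnaires, and that the course feedback form is the written feedback named in 4.2. Existing safeguards lessen the risk without removing it. It does not invalidate the study and leaves the attendance and completion outcomes intact, but the change is cheap enough to make before the first course.

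**What to change.** **In 4.7 and 5.6:** have the FFT and the course feedback form returned in a separate prepaid envelope addressed to the research team and not to the clinic, marked with study ID only. Print on each form that clinicians treating the patient will not see individual answers and that care does not depend on them. Make sure this is true for any treating clinician who is on the research team, for example by withholding identifiable individual answers from that person. The other questionnaires can keep their present route.

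**In 4.8:** where one of the listed moderators neither delivered that course nor helped develop BR, assign that person to moderate and to take part in coding. If nobody on the list qualifies, report the moderators' roles as a limitation of the acceptability findings. An outside moderator would be an extra resource and is not asked for here.

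**Cost:** a second envelope, two sentences on the forms, and one more step to link forms to clinic data. Splitting the pack might slightly affect return rates, which are themselves a feasibility outcome, so report returns separately for each envelope.

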4.8 Questionnaires

Severe Asthma Questionnaire (SAQ) (Appendix 7)

The new questionnaire will provide a combined assessment of disease and its treatment on the quality of life of patients with severe asthma (13). The scale is based on existing HRQoL

scales but modified for the severe population and provides separate assessments of the effect of asthma symptoms and the effect of asthma medicines. The questionnaire has 16 items assessing experience over the last two weeks and was produced from detailed qualitative research. An additional 3 items are included to assess overall QoL during the last two weeks, and QoL during different months of the year

General Symptom Questionnaire (GSQ) (Appendix 8)

The GSQ is a 65 item questionnaire that was designed to measure the symptoms of patients with fibromyalgia, irritable bowel syndrome and chronic fatigue syndrome (12). The questionnaire assesses the frequency of extra-pulmonary symptoms, such as somatic and psychological symptoms, on a 6 point Likert scale (the value scoring for each response shown in brackets): “Never or almost never” (1), “Less than 3 or 4 times per year” (2), “Every month or so” (3), “Every week or so” (4), “More than once per week” (5) or “Every day” (6). This questionnaire was used to measure the number and frequency of extra-pulmonary symptoms reported by patients. The scale measures frequency of symptoms. This questionnaire be completed by potential participants at baseline to identify those that report 8 or more non-respiratory symptoms per week and are eligible to participate. At subsequent time points, participants will complete the GSQ-A.

General Symptom Questionnaire-A (Appendix 9)

This is an abridged GSQ consisting of 16 non-respiratory symptoms that are associated with asthma severity. It uses the same 6 point Likert scale as the full GSQ.

The Positive and Negative Affect Schedule (PANAS) (Appendix 10)

This questionnaire measures positive and negative affect and consists 20 questions in total, 10 measuring positive affect and 10 measuring negative affect. Participants respond to each question by using a 5 point scale where 1 indicates “not at all” and 5 indicates “very much”.

Asthma Control Questionnaire (Asthma Control Questionnaire) (Appendix 11)

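### The first questionnaire set need not be completed before session 1 and is chased for four weeks, so some baseline scores can be given during or after the course

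*Combined protocol and SAP*

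**What the plan says.** Section 4.7 asks participants to complete the questionnaires "when they attend the Body Reprogramming course during the first and last week". Packs go to the home by post and come back by post. If a pack is not returned: "If participants have not returned the questionnaire within two weeks the questionnaire pack will be sent out again". Then: "If a further two weeks pass without the return of questionnaires a researcher will contact participant by phone". These rules do not distinguish the first set from the last.

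Section 4.6 describes the course: "There will be four sessions and each session will consist of a 25-30 minute presentation", each with a "practice and report back next week" task. The sessions are therefore weekly.

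Section 4.8 gives the recall periods. For the SAQ: "The questionnaire has 16 items assessing experience over the last two weeks". For the ACQ: "The questionnaire asks patients to assess their symptoms over the last week". The full GSQ is completed at screening; after that, "At subsequent time points, participants will complete the GSQ-A".

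Section 4.9 estimates pre-to-post mean differences and adds an ANCOVA with the baseline score as covariate. Its missing-data rule deals with missing items, not late forms. It also promises a full SAP before final data extraction. Section 5.6 applies the same questionnaire time points to Phase 2.

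**The concern.** A baseline score should describe the patient before the intervention. Here the first set is due in the week the course starts, and the chase for a slow responder lasts longer than the course. The available text gives no posting day, no start for the two-week clock, no requirement to finish before session 1 and no latest date for a form to count as a baseline. A site that follows section 4.7 exactly can therefore obtain a 'pre' score from someone who has already attended some or all of the sessions.

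At stake are the pre-post differences and the baseline-adjusted analysis in section 4.9. The forms concerned are mainly the SAQ, ACQ and PANAS. The screening GSQ is taken before the course and may supply a clean earlier score for the abridged GSQ-A. Late return of the second pack also matters: it changes the period that the post-course Global Rating of Change Questionnaire (GRCQ) covers, and it delays the Friends and Family Test.

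These scores have a purpose even in a feasibility study. Section 4.2 seeks feedback on whether the questionnaires suit the assessment of improvement in larger studies. Section 5.1 aims to test how the outcome measures perform ahead of a possible randomised trial.

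**Working it through.** The plan states no figure to reproduce. The check is calendar arithmetic.

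**Inputs.** Four weekly sessions (4.6), on days 0, 7, 14 and 21. Re-send after 2 weeks and phone call after 2 more (4.7). Recall of 14 days for the SAQ and 7 days for the ACQ (4.8). Between 12 and 14 participants per phase (4.10, 5.8). Assumptions: the clock starts at posting, and postal delay is ignored.

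**Chasers for the first pack.** With posting on day p, re-send = p + 14 and call = p + 28.

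| Posted (p) | Re-send | Call |
|---|---|---|
| 0 | 14 | 28 |
| -7 | 7 | 21 |
| -14 | 0 | 14 |
| -21 | -7 | 7 |
| -28 | -14 | 0 |

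Only posting more than 28 days ahead puts both chasers before session 1. Nothing in the text asks for that.

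**Overlap of the two packs.** If both packs have the same lead, the last-week pack goes out on day 21 + p. The call about the first pack comes (p + 28) - (p + 21) = 7 days later, so a slow responder can hold both at once. With p = 0, a participant could complete the 'post' form on day 21 and the 'pre' form at the call on day 28. The interval from pre to post is then 21 - 28 = -7 days, against a nominal 21.

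**Recall after session 1.** For a 'pre' form completed on day d, the share of the recall period after session 1 is min(d, 14)/14 for the SAQ and min(d, 7)/7 for the ACQ.
- Day 7: SAQ 7/14 = 50%; ACQ 7/7 = 100%.
- Day 14: both 100%.

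**Illustration only.** Suppose k of n participants complete the first form late, when a fraction f of a common eventual change has already occurred, and all last forms are on time. The mean change then shrinks by k × f/n. With k = 2 (assumed):
- n = 12: from 2 × (1/3)/12 = 5.6% to 2 × 1/12 = 16.7%.
- n = 14: from 4.8% to 14.3%.

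Neither k nor f is in the documents.

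**Should late baselines be dropped?** Work in units of the SD of change, and assume late and on-time participants are exchangeable apart from a shift b in late forms. Keeping all forms has total error sqrt(1/n + (k × b/n)²); dropping the late ones has sqrt(1/(n - k)). Dropping is better only if b > sqrt(n/(k(n - k))).
- n = 12: k = 2 gives 0.77; k = 4 gives 0.61; k = 6 gives 0.58.
- n = 14: k = 2 gives 0.76; k = 5 gives 0.56; k = 7 gives 0.53.

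Dropping 4 of 12 raises the standard error from 1/sqrt(12) = 0.29 to 1/sqrt(8) = 0.35. This bears on the choice of remedy, not on whether the gap exists.

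**The case against.** The strongest case on the other side is about weight. The study is unpowered, section 5.9 declares a significance level not applicable, and willingness to attend and to return forms is measured just as well with late forms. A form completed within week one (days 0 to 6) still has at least 14 - 6 = 8 of its 14 SAQ recall days before session 1. All of this stands and limits the priority. It does not remove the gap: the same SAQ form on day 14 has no recall before session 1, and an ACQ form completed on day 6 has only one of its seven days.

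A second objection is that the promised SAP can deal with late forms. It can set a handling rule. It cannot recover a completion date that was not collected or change when packs were posted.

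Three stronger readings are tempting, and the documents do not support them.
- A reader might infer that BR's effect will be understated. Late baselines alone would tend that way if BR helps, but not for someone who has yet to attend. Late last-week forms can act in either direction.
- A reader might infer that the chasers bound the gap between a participant's two forms, for example at 0 to 49 days. They do not: the order can reverse, and the phone call is not a deadline.
- A reader might infer that no completion date is captured. The questionnaires, the information leaflets and the Gantt chart are not in the available text, so a date box or a stated mailing day cannot be excluded. A date box would reveal late baselines without preventing them.

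**Conclusion.** The point holds at low to moderate weight. On the available text, section 4.7 allows scores treated as baseline in section 4.9 to be completed during or after the course, and even after the participant's own post-course form. No maximum interval is set.

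The calendar days rest on weekly sessions, which the text supports, and on a clock that starts at posting, which it does not state. The general conclusion does not depend on the exact posting day unless packs go out more than four weeks before session 1. No bias figure is offered, because the posting day, the share of late forms and the time course of any improvement are unknown.

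Phase 2 inherits the timing and adds a separate inconsistency. Section 5.6 sets the last questionnaires in the final course week, yet its GRCQ rates change since starting both BR and a biologic. Section 5.3 offers the course while patients wait for that biologic. A post-course form completed after the biologic has started is therefore not purely a matter of late return. These passages need to be reconciled.

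**What to change.** - Change section 4.7 so that the first pack is posted once GSQ eligibility is confirmed, with the reminder and phone call finished before session 1, and ask participants to complete it before that session. One example is posting on day -21, reminding on day -14 and phoning on day -7. Keeping the present two-week intervals would need posting more than 28 days ahead.
- Record the completion date on every form. Report it relative to the sessions and, in Phase 2, to the biologic start.
- Start groups on schedule. Flag late baselines, but keep them in the return rate and the main descriptive summary. Add a sensitivity summary restricted to first forms completed before session 1; a cut-off of on or before that day would admit forms filled in after the session.
- In section 5.6, reconcile the last-week time point with the period that the Phase 2 GRCQ asks about.

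The handling rule can wait for the SAP. The mailing day and the date field must be settled before packs go out.

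Costs: a lead time of about three weeks before each group under the example schedule, chasers one week apart instead of two, and baseline forms up to 21 days old at session 1 when returned at once. In Phase 2 the lead must fit within the existing wait for the biologic; where it does not, the form is dated and flagged as late. Section 6.2 means the change also needs HRA review and local R&D acceptance as a protocol amendment.
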